**Sponsor/Quotient Sciences Confidential**

---

**8.2.1 Criteria for Sentinel Dosing Decisions**

For all cohorts following a sentinel design (Parts 1 and 3) the decision to proceed with the main group will be made by the investigator, based on safety data until 96 h post-dose (Part 1) or 96 h post-final dose (Part 3) in the sentinel participants. The investigator or medically qualified designee who is familiar with the study protocol and IB, and medical monitor or delegate (with approval from the sponsor's medical director or delegate) will decide whether to proceed with dosing the remaining participants in the cohort.

**8.3 Participant Withdrawal**

If a participant wishes to leave the study at any time, they will be permitted to do so. Every reasonable effort will be made by Quotient to complete final assessments/discharge procedures. Quotient will advise the sponsor of the withdrawal of any participant from the study.

Early withdrawal is defined as the date of the decision to withdraw the participant from the study. Participant completion is defined as the date of the last procedure conducted or last contact (e.g. discharge from the study or unscheduled visit) for that participant.

If a participant requests to leave the clinical unit earlier than the planned discharge time e.g. due to unforeseen personal circumstances, but aims to return to the clinical unit to complete the study, this will be documented as a participant self-discharge and a protocol deviation. The participant must complete the planned assessments/discharge procedures before discharge from the clinical unit, and may return for the next study period/assessments, as planned following agreement between the sponsor and the investigator.

Participants in Part 1 will receive a single dose in the study; therefore, after an individual participant has received a dose of IMP, withdrawal of that participant from further dosing is not possible. Participants will be monitored for the criteria listed below, which may require their withdrawal from some or all study procedures if continuation is not in their best interests, except when the withdrawal is a result of withdrawal of consent.

Participants in Parts 2 and 3 will be withdrawn from the study drug for the following reasons:

- Experiencing a serious or severe AE including but not limited to:
  - corrected QT interval by Fridericia's formula (QTcF) of >500 msec or increase in QTcF of >60 msec from baseline (confirmed following a repeat ECG)
  - alanine aminotransferase (ALT) concentration >3 × the upper limit of the reference range (confirmed following a repeat ALT blood test)
- Pregnancy (see [Section 9.5](#))
- Termination of the study
- Upon the participant's request (withdrawal of consent)
- Significant deviation from the protocol
- Concurrent illness that would adversely affect participant safety or data integrity or requirement for prohibited medication
- At the discretion of the investigator

For the purpose of withdrawal criteria, baseline will be considered as the last available assessment prior to first dose.

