#### **8.5 Stopping Criteria**

##### **Cohort stopping rules**

Dose escalation, as well as continued dosing within any given cohort, will be paused and may be halted based on full review of all available clinical safety data if any of the following occur:

- Two or more participants in the same cohort experience an AE assessed as severe
- Two or more participants with QTcF >500 msec and/or an increase in QTcF >60 msec considered related to IMP administration
- At least 2 participants in the same cohort with demonstrated recurrent or persistent post-dose orthostatic hypotension (i.e., either a drop of systolic blood pressure [SBP]  $\geq$ 20mmHg or diastolic blood pressure [DBP]  $\geq$ 10mmHg after 3 min standing) and/or symptomatic hypotension (lightheadedness, weakness, blurry vision, dizziness or fainting upon standing) requiring medical intervention

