##### **Overall study stopping rules**

Enrolment into the study will be placed on hold and dosing will be halted if any of the following occur cumulatively across all of the cohorts

- At least one IMP-related SAE
- Two severe non-serious adverse reactions considered as, at least, possibly related to the IMP administration in two subjects in the same cohort, independent of within or not within the same system-organ-class are observed.
- The investigator and/or the study sponsor considers that the number and/or severity of AEs, abnormal safety monitoring test, or abnormal laboratory findings justify putting the study on hold.

Relatedness to IMP will be determined by the investigator.

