## **14 Assessment of Safety**

### **14.1 Definition and Classification of Adverse Events**

An AE is any untoward medical occurrence in a participant that occurs either before dosing (referred to as a pre-dose AE) or once a medicinal product has been administered, including occurrences which are not necessarily caused by or related to that product.

An adverse drug reaction is any AE where a causal relationship with the IMP is at least a reasonable possibility (related).

AEs will be monitored from the time the participant signs the ICF until the end of study visit. The severity of AEs should be assessed as follows:

**Mild** An AE that is easily tolerated by the participant, causes minimal discomfort and does not interfere with everyday activities

**Moderate** An AE that is sufficiently discomforting to interfere with normal everyday activities; intervention may be needed

**Severe** An AE that prevents normal everyday activities; treatment or other intervention usually needed

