**14.5.10 Abnormal Laboratory Findings**

In cases where laboratory findings are outside the normal range and the investigator believes that the results may be of clinical significance, repeat sampling may be requested as clinically indicated. If the abnormal finding is clinically significant, appropriate actions will be taken e.g. the participant will not be entered into the study or the participant may be withdrawn from the study. The participant will be referred to their general practitioner or other appropriate provider for further care if necessary. The same will apply if the results of the HBsAg, HCV Ab or HIV test are positive and in addition the investigator will ensure that adequate counselling is available if requested.

Abnormal results at any unscheduled follow-up assessments will also require repeat testing if the investigator believes the results may be of clinical significance.

Any clinically significant abnormality, including changes from baseline, must be reported as an AE.

Additional blood and/or urine samples may be taken for safety tests. Furthermore, additional assays outside those specified in the protocol may be performed for safety reasons as requested by the investigator or sub-investigator.

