#### **11.3.1.1 Overall Summary of Adverse Events**

The following will be summarised by treatment and overall, in Part 2, and by all placebo, all active, and each dose level in Part 1 and Part 3 for the safety analysis set:

- Number and percentage of subjects reporting at least 1 TEAE
- Number and percentage of subjects reporting severe TEAEs
- Number and percentage of subjects reporting IMP-related TEAEs
- Number and percentage of subjects reporting serious TEAEs
- Number and percentage of subjects reporting TEAEs leading to participant withdrawal
- Number and percentage of subjects reporting TEAEs leading to death
- Total number of TEAEs
- Total number of severe TEAEs
- Total number of IMP-related TEAEs
- Total number of serious TEAEs
- Total number of TEAEs leading to participant withdrawal
- Total number of TEAEs leading to death

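### Section 8.3 calls ALT and QTcF outliers serious or severe AEs, but the severity scale in 14.1 has no grade for them, so the stopping rules in 8.2.2 and 8.5 can disagree on the same findings

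*Protocol*

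**What the plan says.** **Withdrawal (Protocol 8.3).** Participants in Parts 2 and 3 come off study drug for "Experiencing a serious or severe AE including but not limited to" a confirmed QTcF above 500 msec or a rise above 60 msec, and a confirmed ALT above 3 times the upper limit of the reference range. In Part 1 the same criteria are monitored. None of the limits requires symptoms.

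**Severity scale (Protocol 14.1).** Mild is "An AE that is easily tolerated by the participant, causes minimal discomfort and does not interfere with everyday activities". Moderate and severe are defined by increasing interference with activities, with intervention possibly needed (moderate) or usually needed (severe). No laboratory or ECG value appears in the scale. SAP 11.3 uses the same three classes and adds no definition.

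**Reporting (Protocol 14.5.10).** "Any clinically significant abnormality, including changes from baseline, must be reported as an AE". Section 14.7 says the same for ECG findings.

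**Stopping rules.**
- 8.5, cohort: dosing and escalation pause if "Two or more participants in the same cohort experience an AE assessed as severe". Causality is not a condition. A separate cohort rule names the QTcF limits directly, for cases considered related.
- 8.5, overall: dosing halts on "Two severe non-serious adverse reactions considered as, at least, possibly related to the IMP administration" in two participants of one cohort, or on one related SAE.
- 8.2.2 (repeated in SAP 5.2.2): the study is halted, with a reference to 8.5, once two participants at one dose level or in one cohort have a related non-serious AE that is either severe or clinically significant.
- 8.6 points to 8.5 for the definition of serious or severe AEs. Section 8.5 gives triggers, but does not say what makes an event severe.

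**Outputs.** SAP 11.3.1.1 reports "Number and percentage of subjects reporting severe TEAEs", and SAP 11.3.1.3 tabulates TEAEs by maximum severity.

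**The concern.** Section 8.3 treats certain numeric findings as members of the class of serious or severe AEs. Section 14.1, which tells the investigator how to grade, gives no route by which a number alone becomes severe. A healthy volunteer with ALT above the 8.3 limit and no complaints fits the description of mild more readily than that of severe. The rules in 8.5 then act on the word severe, and nothing says whether the 8.3 list feeds into it.

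In a first-in-human escalation, the stopping rules should give one answer on one set of data. ALT is the sharper case, because 8.5 has no ALT rule of its own. A halt is also costly to reverse: 8.5 requires a substantial amendment to declare it and another, approved, to resume. AE incidence is part of the primary endpoint, so the severity tables carry the same uncertainty.

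**Working it through.** The question is mainly one of text, so I set the rules against four cases. In each, two participants in one cohort have confirmed, asymptomatic, non-serious findings that meet an 8.3 limit and are reported as clinically significant AEs. Each case is read twice: with 8.3 setting the grade (severe) and with 14.1 setting it (not severe).

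| Case | Grade set by | 8.2.2 halt | 8.5 cohort pause | 8.5 overall halt, severe rule |
|---|---|---|---|---|
| ALT, both related | 8.3 | yes | yes | yes |
| ALT, both related | 14.1 | yes (clinically significant) | no | no |
| ALT, not related | 8.3 | no | yes | no |
| ALT, not related | 14.1 | no | no | no |
| QTcF, both related | 8.3 | yes | yes | yes |
| QTcF, both related | 14.1 | yes (clinically significant) | yes (QTcF rule) | no |
| QTcF, not related | 8.3 | no | yes | no |
| QTcF, not related | 14.1 | no | no | no |

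Three results follow.

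1. For related ALT cases graded by 14.1, 8.2.2 says halt, while the severe rule in 8.5, the section it cites, is not met.
2. For ALT cases not judged related, the cohort pause depends wholly on which section sets the grade.
3. For related QTcF cases the pause occurs either way. Only the severe-based overall halt in 8.5, and the pause for unrelated cases, stay ambiguous.

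There is a further branch. Section 8.3 says serious or severe without saying which. If a related finding were taken as serious, a single case would meet the SAE rule. Section 14.4.1 leaves that to the investigator's view of what is an important medical event.

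**Effect on the tables.** Two affected active participants in a Part 1 or Part 3 dose group are 2/6 = 33%, counted as 2/6 or 0/6 severe. Part 2 has 8 participants, all on active, so two are 2/8 = 25%.

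**How often two cases might arise (illustration only).** Protocol 15.1 gives the chance of at least one AE among 6 as 47%, 62%, 74% and 82% at true rates of 10%, 15%, 20% and 25%. The formula 1 − (1 − p)^6 gives 46.9%, 62.3%, 73.8% and 82.2%, so these figures reproduce. If the same rates applied to ALT above the 8.3 limit, the chance of two or more among 6 would be 1 − (1 − p)^6 − 6p(1 − p)^5 = 11.4%, 22.4%, 34.5% and 46.6%. With 8 participants it would be 18.7%, 34.3%, 49.7% and 63.3%. The documents give no ALT rate, and 15.1 refers to any AE. These figures show how often the two-case situation would occur under a borrowed rate. They are not the chance of a wrong decision.

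**The case against.** A reader might infer something stronger: that severity grade is the only numeric route from ALT to a stopping rule, so that two related cases either halt the study or trigger nothing mandatory. The documents do not support this. Section 8.2.2 halts for two related non-serious AEs that are clinically significant, whatever their grade, and 14.5.10 makes clinical significance the ground for reporting a laboratory abnormality as an AE. Related cases reported on that ground therefore halt under either reading. Nor does the grade alone decide escalation in Part 1. The 8.2.2 rule sits among the dose-decision rules, the committee must review all data including safety laboratory results, and the discretionary hold in 8.5 expressly covers abnormal laboratory findings.

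It can also be said that only one grade is ever recorded. Section 14.1 says how to assess it, 8.5 acts on what was assessed, the SAP tabulates what was recorded, and 8.3 concerns individual withdrawal. The scale also has an intervention limb, so an asymptomatic finding that leads to withdrawal is not automatically mild.

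Much of this stands. The consequence is limited by 8.2.2, the QTcF effect is narrow, and Section 6.4.1 lists no hepatic risk that would support an assumed ALT rate. It does not remove the conflict. An investigator who follows 8.3 records severe, one who follows 14.1 normally would not, and no sentence ranks the two. The width of 8.2.2 also adds a disagreement with 8.5 instead of settling the grade.

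**Conclusion.** The point holds as an inconsistency in the current text. For ALT, two related, clinically significant, non-severe cases meet the halt in 8.2.2 but not the severe rule in 8.5. Two cases of any causality do or do not pause the cohort, depending on whether 8.3 or 14.1 sets the grade. For QTcF the ambiguity is confined to the severe-based overall halt in 8.5 and to cases not judged related. Severe-TEAE counts move with the same choice, for example between 2/6 and 0/6 in a Part 1 or Part 3 dose group. The reference in 8.6 does not help, because 8.5 contains no definition.

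This assumes that the findings are asymptomatic, non-serious and judged clinically significant, and that an investigator using 14.1 alone would not grade them severe. It does not show that a related ALT signal could pass every mandatory rule. No sample size or error rate is affected.

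**What to change.** Reconcile Protocol 8.2.2, 8.3, 8.5, 8.6 and 14.1, with SAP 5.2.2 and 11.3, in one of two ways:

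- State once whether laboratory and ECG findings that meet the 8.3 limits count as severe (or serious) for the stopping rules, and have every section refer to that statement.
- List the 8.3 limits as stand-alone withdrawal criteria, not as examples of a serious or severe AE, and state whether they count towards 8.2.2 and 8.5.

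In either case, make the halt wording in 8.2.2 and 8.5 agree, correct the reference in 8.6, and use the same convention in the SAP severity tables. Which clinical rule applies is for the sponsor to decide.

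The cost is a few sentences in the protocol, probably as a substantial amendment because stopping rules are touched, and small matching edits to the SAP. No new data are needed.

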**Sponsor/Quotient Sciences Confidential**

---

For a participant who withdraws because of an IMP-related AE, every effort will be made to ensure the participant completes discharge procedures.

Early withdrawal for safety reasons will be distinguished from withdrawal of consent by the participant to participate in any further activities.

#### **8.4 Participant Replacement**

In Part 1, up to 2 replacement participants may be used per cohort. The maximum number of participants that may be dosed is 50 (8+2 per cohort).

In Part 2, up to 4 replacement participants may be enrolled into the study. The maximum number of participants that may be dosed in Part 2 is 12 (8+4).

In Part 3, up to 2 replacement participants per cohort (if optional cohorts are utilised) may be enrolled into the study. The maximum number of participants that may be dosed is 30 (8+2 per cohort).

Any participant withdrawn due to an IMP-related AE will not be replaced.

Participants withdrawing for other reasons may be replaced as required by agreement between the investigator and sponsor to ensure sufficient evaluable participants.

#### **8.5 Stopping Criteria**

##### **Cohort stopping rules**

Dose escalation, as well as continued dosing within any given cohort, will be paused and may be halted based on full review of all available clinical safety data if any of the following occur:

- Two or more participants in the same cohort experience an AE assessed as severe
- Two or more participants with QTcF >500 msec and/or an increase in QTcF >60 msec considered related to IMP administration
- At least 2 participants in the same cohort with demonstrated recurrent or persistent post-dose orthostatic hypotension (i.e., either a drop of systolic blood pressure [SBP]  $\geq$ 20mmHg or diastolic blood pressure [DBP]  $\geq$ 10mmHg after 3 min standing) and/or symptomatic hypotension (lightheadedness, weakness, blurry vision, dizziness or fainting upon standing) requiring medical intervention

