**9.3 Exclusion Criteria****Medical/Surgical History and Mental Health**

1. Serious adverse reaction or serious hypersensitivity to any drug or the formulation excipients
2. Presence or history of clinically significant allergy requiring treatment, as judged by the investigator. Hay fever is allowed unless it is active
3. History of clinically significant cardiovascular, renal, hepatic, dermatological, chronic respiratory or gastrointestinal disease, neurological or psychiatric disorder, as judged by the investigator
4. Blood pressure (supine) at screening or admission outside the range of 90 to 140 mmHg systolic or 50 to 90 mmHg diastolic; and pulse rate outside the range of 45 to 100 bpm, unless deemed not clinically significant by the investigator
5. A decrease of SBP  $\geq$ 20 mmHg after 3 min standing and/or a decrease of DBP  $\geq$ 10 mmHg after 3 min standing, at screening (applies to Part 1 and Part 3 only)
6. History or presence of known structural cardiac abnormalities, family history of long QT syndrome, cardiac syncope or recurrent, idiopathic syncope, exercise related clinically significant cardiac events. Any clinically significant abnormalities in rhythm, conduction or morphology of resting ECG or clinically important abnormalities that may interfere with the interpretation of QT interval changes
7. Presence of sinus node dysfunction, clinically significant PR interval prolongation ( $>210$  msec), intermittent second- or third-degree atrioventricular block, complete bundle branch block, sustained cardiac arrhythmias including (but not limited to) atrial fibrillation or supraventricular tachycardia; any symptomatic arrhythmia with the exception of isolated extra systoles, abnormal T wave morphology which may impact on the QT/QTc assessment, or QTcF  $>450$  msec. Participants with borderline abnormalities may be included if the deviations do not pose a safety risk, and if agreed between the sponsor's medical monitor and the investigator
8. Participants with a history of cholecystectomy or gall stones
9. Participants with conditions that affect their ability to smell or taste (Part 1 only) including, but not limited to mouth ulcers, gum disease, nasal surgery and smell and/or taste disorders (e.g. dysosmia, dysgeusia, respiratory and/or sinus infection or cold)

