**14.6 Vital Signs Measurements**

Blood pressure and heart rate will be measured by an automated recorder after the participant has been in a supine position for a minimum of 5 min and oral temperature and respiratory rate will be measured according to the time schedules presented in [Appendix 2](#)[Appendix 5](#), [Appendix 6](#) and [Appendix 7](#).

Blood pressure and heart rate orthostatic measurements will also be taken according to the time schedules presented in [Appendix 5](#), [Appendix 6](#) and [Appendix 7](#). Two measurements will be recorded; 1 supine and 1 standing. The first supine measurement will be performed after the participant has rested in a supine position for at least 5 min. The second blood pressure and heart rate measurements will be performed after the participant has been standing for at least 3 min but no more than 5 min. Orthostatic hypotension will be defined as either:

- A decrease of SBP  $\geq$  20 mmHg after 3 min standing, or
- A decrease of DBP  $\geq$  10 mmHg after 3min standing

The acceptable deviations from the nominal vital signs measurement time points are:

- Day 1 in all parts and Day 8 in Part 2: The pre-dose vital signs measurements will be taken  $\leq$  2 h before dosing
- On Days 2 and 3 (Part 3 only): the pre-dose vital signs measurements will be taken  $\leq$  1 h before dosing.
- Post-dose vital signs measurements will be taken  $\pm$  15 min from the nominal post-dose time point.
- For return visits, vital signs measurements will be taken  $\pm$  2 h from the nominal return visit time point.
- End of study visit vital signs measurements will be taken  $\pm$  1 day from the nominal time point.

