p Sample will be taken prior to IMP administration (≤2 h before dosing).

**Appendix 5      Part 1 (All Cohorts) Safety and Pharmacokinetic Assessment Time Points  
(Days 1 to 7)**

Study Day	Time point	Plasma PK	Urine PK a	Safety Labs and Urinalysis	Holter Extractions	Vital Signs b	Orthostatic Vital Signs	Single 12-lead ECGs	Triplicate 12-lead ECGs
1	-1.5 h				X			X	
	-1 h				X			X	
	Pre-dose (-0.5 h)	X	X		X	X	X	X	
	0 h		0 to 6 h						
	0.5 h	X			X	X		X	
	1 h	X			X			X	
	2 h	X			X	X	X	X	
	3 h	X			X			X	
	4 h	X			X	X	X	X	
	5 h	X						X	
	6 h	X	6 to 12 h		X	X		X	
	8 h	X			X	X		X	
	10 h					X			
	12 h	X	12 to 24 h		X	X	X	X	
2	24 h	X	24 to 48 h	X	X	X	X		
3	48 h	X	48 to 72 h			X			X
4	72 h	X				X			X
5	96 h	X		X		X			X
7	144 h	X		X		X	X		X

a Part 1, Cohorts 1C and 1D only.

b Blood pressure, heart rate and respiratory rate at all time points.

Allowable windows for PK blood sampling, vital signs assessments and ECGs can be found in: [Sections 13.1, 14.6 and 14.7](#).

**Sponsor/Quotient Sciences Confidential****Appendix 6      Part 2 Safety and Pharmacokinetic Assessment Time Points (Days 1 to 14)**

Study Day	Time point	Plasma PK	Safety Labs and Urinalysis	Holter Extractions	Vital Signs a	Single 12-lead ECGs	Triplicate 12-lead ECGs
1	-1.5 h			X		X	
	-1 h			X		X	
	Pre-dose (-0.5 h)	X		X	X	X	
	0 h						
	0.5 h	X		X	X	X	
	1 h	X		X		X	
	2 h	X		X	X	X	
	3 h	X		X		X	
	4 h	X		X	X	X	
	5 h	X					
	6 h	X		X	X	X	
	7 h						
	8 h	X		X	X	X	
	10 h				X		
	12 h	X		X	X	X	
2	24 h	X	X	X	X	X	
3	48 h	X			X		X
4	72 h	X			X		X
5	96 h	X	X		X		X
7	144 h	X	X		X		X
8	-1.5 h			X		X	
	-1 h			X		X	
	Pre-dose (-0.5 h)	X		X	X	X	
	0 h						
	0.5 h	X		X	X	X	
	1 h	X		X		X	
	2 h	X		X	X	X	
	3 h	X		X		X	
	4 h	X		X	X	X	
	5 h	X					
	6 h	X		X	X	X	
	7 h						

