## 11.5 Vital Signs

For each study part, the details of measurement of supine vital signs (i.e., systolic and diastolic BP, and heart rate) and non-supine vital signs (oral temperature and respiratory rate) will be measured at each scheduled timepoint.

Systolic and diastolic BP and heart rate orthostatic measurements will also be taken (1 supine and 1 standing) according to the time schedules presented in [Appendix 4](#) (Part 1), [Appendix 5](#) (Part 2) and [Appendix 6](#) (Part 3). Vital signs parameters will be reported in the order given above, i.e., both summary tables and data listings.

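### The orthostatic stopping rule in Protocol 8.5 covers Part 2, and Protocol 14.6 and the SAP say orthostatic readings are taken there, but no Part 2 schedule contains one

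*Protocol*

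**What the plan says.** **The rule.** Protocol 8.5, cohort stopping rules: "Dose escalation, as well as continued dosing within any given cohort, will be paused and may be halted" if any listed event occurs. The third event is "At least 2 participants in the same cohort with demonstrated recurrent or persistent post-dose orthostatic hypotension", specified as a drop of at least 20 mmHg systolic or 10 mmHg diastolic after 3 minutes standing. It is joined by and/or to "symptomatic hypotension (lightheadedness, weakness, blurry vision, dizziness or fainting upon standing) requiring medical intervention".

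**Text placing the measurement in Part 2.** Protocol 14.6: "Blood pressure and heart rate orthostatic measurements will also be taken according to the time schedules presented in" Appendices 5, 6 and 7. Appendix 6 is headed "Part 2 Safety and Pharmacokinetic Assessment Time Points (Days 1 to 14"). SAP 11.5 says blood pressure and "heart rate orthostatic measurements will also be taken (1 supine and 1 standing) according to the time schedules presented in" its Appendices 4, 5 and 6, and labels Appendix 5 as Part 2. SAP 11.5.1 promises vital-sign summaries that include the orthostatic data for every study part, by treatment in Part 2. Protocol 6.4.1 promises orthostatic evaluations in the study without excepting any part.

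**Text leaving it out of Part 2.** Protocol Appendices 3 and 6 and SAP Appendices 2 and 5 have no orthostatic row or column. Exclusion criterion 5 (Protocol 9.3), on an orthostatic drop, is assessed "at screening (applies to Part 1 and Part 3 only").

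**The concern.** A stopping rule needs data to act on. In Cohort 2A the rule has a real decision to inform, because each participant receives a second dose on Day 8. The plan followed exactly would produce no standing blood pressure in that cohort, so the measured limb would have no scheduled input. The SAP would also promise a Part 2 summary of data that the schedule never collects. Since criterion 5 does not apply to Part 2, participants with an orthostatic drop at baseline may enter that cohort under a rule that still counts post-dose drops. In a first-in-human study, the safety committee and the site should not have to guess whether a pre-specified criterion is active in a given cohort.

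**Working it through.** The documents state no figure for the performance of this rule, so there is none to reproduce. The check is a count of scheduled assessments and a comparison of the texts.

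**1. Does the rule reach Part 2?** Yes. Section 8.5 speaks of any given cohort, and 8.1.2 gives Cohort 2A two doses (Days 1 and 8), so continued dosing within the cohort is a live question there.

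**2. Scheduled orthostatic time points from Day 1 onward**

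| Part | Source | Time points | Total | After first dose |
|---|---|---|---|---|
| 1 | Protocol Appendix 5 | pre-dose, 2, 4, 12, 24, 144 h | 6 | 6 − 1 = 5 |
| 2 | Protocol Appendix 6 | none in either period | 0 | 0 |
| 3 | Protocol Appendix 7 | Day 1: pre-dose, 2, 4, 6, 12 h; Day 2: pre-dose; Day 3 dose: pre-dose, 2, 4, 6, 12, 24, 144 h | 5 + 1 + 7 = 13 | 13 − 1 = 12 |

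**3. Could the Part 2 column have been lost in extraction?** Unlikely. Four separate Part 2 tables, two in each document, agree. So do the footnotes: the vital-signs footnote to Appendix 2 (Part 1) mentions orthostatic time points, and the corresponding footnote to Appendix 3 (Part 2) mentions vital signs only.

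**4. Can the ordinary Part 2 vital signs substitute?** No. Section 14.6 defines routine blood pressure and heart rate as supine, which cannot show a fall on standing.

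**5. Illustration of what scheduled readings could detect.** The documents give no rate of qualifying falls, so assume a per-participant probability p. Assume also 8 independent participants, all on active drug, with every qualifying fall detected. Then P(at least 2 of 8) = 1 − (1 − p)^8 − 8p(1 − p)^7.

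| Assumed p | If measured | From the Part 2 schedule as written |
|---|---|---|
| 5% | 5.7% | 0 |
| 10% | 18.7% | 0 |
| 20% | 49.7% | 0 |
| 30% | 74.5% | 0 |

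For example, at p = 10%: 1 − 0.4305 − 0.3826 = 0.187. The last column covers scheduled data only. It is not the probability that the whole bullet, or stopping in general, is triggered.

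**The case against.** The strongest reply is that the omission is deliberate. Every Part 2 schedule leaves the measurement out, criterion 5 is confined to Parts 1 and 3, and the Version 3.0 change summary lists the specification of that criterion's parts among corrections of errors and inconsistencies. On this reading, 14.6 and SAP 11.5 carry stale cross-references and 8.5 merely lacks a scope statement. That is plausible, but it concedes the point: the texts still disagree, and nothing in them says which governs.

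A reader might infer that the measured limb can never trigger in Part 2. The documents do not support that. Section 14.6 allows additional vital-sign measurements at the investigator's discretion, and 14.13 allows extra non-invasive procedures already in the protocol when an important drug effect is suspected. Such readings could meet the limb. They would probably follow symptoms, however, and recurrence or persistence is hard to demonstrate without repeated standing readings.

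A reader might also infer unmonitored higher exposure in the fed state. Protocol 8.2.2 requires a Part 1 dose level with acceptable safety and a mean exposure that Part 2 is not anticipated to exceed, allowing for 100% bioavailability with food. Section 6.2 expects 400 mg fed to stay below 750 mg fasted. This stands as mitigation, although it is a prediction about the food effect that the cohort exists to measure. The gap is also not confined to the fed state: neither period has the measurement.

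Other protections stand too: the symptomatic limb, the severe-AE and QTcF criteria, and the study-level discretion in 8.5 to hold for an abnormal safety monitoring test. The requirement for medical intervention might also be read as qualifying both limbs, in which case a qualifying participant would already be under care.

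**Conclusion.** The contradiction is confirmed. Section 8.5 covers Cohort 2A, and Protocol 14.6, SAP 11.5 and SAP 11.5.1 describe orthostatic data from Part 2, but the Part 2 schedules provide 0 assessments over two doses in 8 (at most 12) participants, against 5 post-dose in Part 1 and 12 in Part 3. The measured limb and the SAP's Part 2 orthostatic summary have no scheduled input. What is exposed is narrow: recurrent or persistent falls without symptoms, which would probably be missed. Symptomatic cases and the other criteria remain covered.

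A further inference, that an empty Part 2 summary would be taken as absence of events, is speculation. The SAP table index lists only a general vital-signs table for Part 2, and its shell has no orthostatic section.

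The conclusion rests on the appendix tables being complete as reproduced, which their mutual agreement supports. It does not depend on the assumed rates in the illustration.

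**What to change.** Reconcile the following so that the scope of the measured limb, the Part 2 schedule, eligibility and the reporting agree: Protocol 6.4.1, 8.5, 9.3 (criterion 5), 14.6 and Appendices 3 and 6; SAP 11.5, 11.5.1 and Appendices 2 and 5. The sponsor decides which version is intended. This review takes no position on the clinical rule.

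If the schedules reflect the intent, the cost is wording in 6.4.1, 8.5, 14.6 and the SAP. If the text reflects the intent, the cost is schedule entries and supine and standing readings, which could use vital-sign times and equipment already planned in Part 2, plus a decision on criterion 5.

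Three related slips can be settled in the same edit. Protocol Appendix 4, footnote n, sends the Part 3 reader to Appendix 6 for orthostatic times that stand in Appendix 7. SAP 11.5.1 counts falls of more than 20 or 10 mmHg where the protocol uses at least 20 or 10 mmHg. SAP 11.5.1 also refers to the mean of duplicate supine readings, where 14.6 specifies one.
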